##### Dates for adverse event and concomitant medication

Missing or partial start dates for AEs and concomitant medication data will be handled in the following way:

- If the start date is totally missing, the date will still be missing.
- If the start date is partial where only month and year are given, then the two cases are considered:
  1. If the available partial date (month and year) is before the month and year of treatment start date, then the AE/medication will be considered as pre-treatment and the date will be imputed as the end date of the month.
  2. If the available partial date does not indicate that the AE/medication has started before the treatment start, then the AE/medication will be considered as treatment emergent/concomitant or post-treatment emergent, as follows:
    - If month is same as month of treatment start date or the month right after the month of treatment start date, then the AE is treatment emergent.
    - Else if month is after month of treatment start date, then the AE is post-treatment emergent.
    - For medications, if the available partial date does not indicate that the medication has started before the treatment start, then it will be considered as concomitant.

The date will be imputed as the start (1st) of the month (if the month and year is after the month and year of the treatment start date) or treatment start date (if the month and year is same as month and year of the treatment start date).

- If the start date is partial where only the year is given, then the two cases are considered:
  3. If the available partial date (year) is clearly before the year of treatment start date, then the start date is imputed as last day of the year (i.e. 31 December).
  4. If the available partial date (year) is equal to or after the year of treatment start date, then the start date will be imputed as start of the year (1st January YYYY) (if the year is not same as that of the treatment start date) or treatment start date (if the year is same as the treatment start date).
- For the partial end dates, similar procedure will be used as for the start dates. The only difference is the imputation for missing days and months. Missing days is imputed to the end of the month (instead of the start of the month) or at the date of study discontinuation/completion, whichever occurs first. If only year is available, the end date is set to 31st December YYYY or at the date of study discontinuation/completion, whichever occurs first. It will be checked that the imputed end dates fall after the corresponding start dates.

All completely missing end dates will be missing.

The partial dates as reported will be presented in the listings. The imputed dates purpose is for deriving the corresponding flags for relation to start/end of IMP (e.g. TEAE flagging) and study days, when applicable.

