#### **5.6 Concomitant Medication and Therapies**

Concomitant medication and/or other therapy considered necessary for the subject's welfare may be given at the discretion of the investigator. All concomitant medication and other therapy, including e.g. premedication, prophylactic antibiotics and PE, must be recorded on

the concomitant medication page in the eCRF throughout the study, beginning from screening to end of study. Treatments up to 30 days prior to screening will be recorded in the eCRF. Recorded information will include indication, name of drug, dose (if available), route of administration and start and stop date.

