## 4.4 Demographics and other baseline characteristics

The demographics are age at screening date, sex, and race.

Medication will be classified according to WHODrug Global B3 dictionary version 2018Q3.

Summary tables will be performed for:

- Demographics (including age (years), sex, race, height, weight and BMI before IMP intake)
- Medical history or concomitant illness as reported at study entry
- Baseline GBS characteristics and GBS symptoms, including:
  - Presence of diarrhoea (<4 weeks from screening)
  - Onset of weakness due to GBS
  - Days from onset of weakness until imlifidase administration
  - GBS variant type at screening
  - Electrophysiology classification of subtype the subject has according to JJ Sejver et al. (Vaccine 2011; 29: 599-612)
  - Status of cranial involvement
  - Medical history of disease affecting mobility (yes/no)

- Medical history of disease affecting respiration (yes/no)
- Pre-medication to prevent/minimise risk of infusion reactions (methylprednisolone and antihistamine or an equipotent antihistamine) before imlifidase infusion
- Medication to minimise the risk for bacterial infections (prophylactic antibiotics), summarizing all prophylactic antibiotics the subjects had during the first 14 days after imlifidase administration (including prophylactic antibiotics given in day before imlifidase administration and in same day as the imlifidase administration).
- Prior medication, summarizing all medications the subjects had before the study (prior to start of study treatment)
- Concomitant medication, summarizing all medications the subjects had throughout the study (following start of study treatment), considering the following tables:
  - All concomitant medications
  - Concomitant medication during Day 1 – 29
  - Concomitant medications during Day 30 – End of study

Note: prior and concomitant medication will exclude ‘Pre-medication to prevent/minimise risk of infusion reactions before imlifidase infusion’ and ‘Medication to minimise the risk for bacterial infections’.

Listings will be provided including the values for each subject of:

- Subject disposition (enrolled, completed, withdrawn (reason for withdrawal) for each analysis set (FAS, SAF and PKPDAS).
- Demographics (including age (years), sex, race)
- Medical history as reported at study entry (system organ class (SOC) and preferred term (PT))
- GBS disease information at study entry
- Baseline GBS characteristics

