### 4.8.1 Adverse events

According to the protocol, an AE is defined as the development of an undesirable medical condition or the deterioration of a pre-existing medical condition following or during exposure to a pharmaceutical product, whether or not considered causally related to the product. Relationship to the study drug will be deemed as not related, unlikely, possible or probable. An undesirable medical condition can be symptoms (e.g., nausea and chest pain), signs (e.g., tachycardia and enlarged liver) or the abnormal results of an investigation (e.g., laboratory findings and electrocardiograms).

A pre-treatment adverse event is any untoward medical occurrence arising or observed between signing of informed consent and administration of the IMP.

A treatment emergent adverse event (TEAE) is any AE occurring after the start of administration of the IMP and within the time of residual drug effect, or a pre-treatment AE or pre-existing medical condition that worsens in intensity after start of administration of the IMP and within the time of residual drug effect.

The time of residual drug effect is the estimated period after the administration of the IMP, where the effect of the product is still considered to be present based on pharmacokinetic, pharmacodynamic or other substance characteristics. The residual drug effect is generally accepted to be 5 times the terminal half-life. The terminal half-life of imlifidase is expected to be within the range of approx. 100 hours, i.e. in this study the residual drug effect is likely to be well within the Day 29 assessments, but since this is the first administration of imlifidase to GBS subjects, all AEs occurring up to Day 29 are regarded as treatment emergent.

A Serious Adverse Event (SAE) is defined as an AE which fulfills any of the following:

- Results in death
- Is immediately life-threatening
- Requires in-patient hospitalization or prolongation of existing hospitalization

- Results in persistent or significant disability or incapacity
- Is a congenital abnormality or birth defect
- Is an important medical event that may jeopardize the patient or may require medical intervention to prevent one of the outcomes listed above. Examples of such events include allergic bronchospasm requiring intensive treatment in an emergency room or at home, blood dyscrasias or convulsions that do not result in inpatient hospitalization, or the development of drug dependency or drug abuse.

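### The month-only start-date rule in SAP 4.1.3 ignores recorded stop dates and the Day 29 limit, so a few records can be classed against the SAP's own definitions

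*SAP*

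**What the plan says.** SAP 4.1.3 (Dates for adverse event and concomitant medication) handles starts reported as month and year only. An earlier month than dosing counts as pre-treatment. Otherwise:

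- **Drugs**, with concomitant as the resulting class: "For medications, if the available partial date does not indicate that the medication has started before the treatment start, then it will be considered as".
- **Adverse events**, with treatment emergent as the resulting class: "If month is same as month of treatment start date or the month right after the month of treatment start date, then the AE is". Any later month is post-treatment emergent.
- **Imputed date:** the 1st of the reported month if that month is later than dosing, or "treatment start date (if the month and year is same as month and year of the treatment start date").

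The section adds that imputed dates serve to derive the flags, naming TEAE flagging as its example. It contains one consistency check: "It will be checked that the imputed end dates fall after the corresponding start dates".

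Three other places set what the rule should deliver. SAP 4.4 separates prior medication, taken before study treatment started, from "Concomitant medication, summarizing all medications the subjects had throughout the study (following start of study treatment"), and plans a separate table for Days 1 to 29. SAP 4.8.1 sets the end of the treatment-emergent period: "all AEs occurring up to Day 29 are regarded as treatment emergent". Protocol 5.6 collects start and stop dates and looks back before the study: "Treatments up to 30 days prior to screening will be recorded in the eCRF".

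**The concern.** A default is reasonable when a partial date leaves the timing open. This rule also applies when the recorded data settle the timing.

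For a drug, a full stop date before the infusion proves that the drug was not taken after it. The rule does not use that date. Treatments from the 30 days before screening are recorded, so month-only starts in the dosing month can arise. A course finished before dosing could then appear in the concomitant tables, including the one for Days 1 to 29, as though given together with imlifidase.

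For an adverse event, the rule uses calendar months while the definition uses study days. For some dosing dates the two cannot agree. The SAP then gives two answers for the same event, one from the flag and one from the imputed date, and two programmers could produce different TEAE and ADR tables.

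**Working it through.** The plan states no figure for this point, so the rule was applied to concrete dates and then to every possible dosing date.

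**Drug example.** Imlifidase on 20 March 2022; start reported as March 2022; recorded stop 15 March 2022.

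- The start month equals the dosing month, so the class is concomitant and the imputed start is 20 March (Day 1).
- The imputed start is 20 − 15 = 5 days after the recorded stop. Duration as stop − start + 1 is 15 − 20 + 1 = −4 days.
- Under SAP 4.4 the drug is prior medication, because all of its use came before study treatment.
- The SAP's check does not cover this record. The stop date is complete, so it was not imputed. The check also states no remedy.

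**Adverse event rule.** Let the dosing day be day d of a month with L days, and let dosing be Day 1. Day 29 is then the dosing date + 28. The 1st of the next month is study day L − d + 2. The whole next month lies after Day 29 when L − d + 2 > 29, that is, when d ≤ L − 28.

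| Month length | Affected dosing days | Study day of the next 1st |
|---|---|---|
| 31 | 1, 2, 3 | 32, 31, 30 |
| 30 | 1, 2 | 31, 30 |
| 29 | 1 | 30 |
| 28 | none | – |

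- Ordinary year: 7 × 3 + 4 × 2 = 29 of 365 dates (7.9%).
- Leap year: 29 + 1 = 30 of 366 (8.2%).
- Example: imlifidase on 2 March 2022, so Day 29 is 30 March. An event reported as April 2022 began on 1 April at the earliest, which is Day 31 − 2 + 2 = 31. The rule flags it treatment emergent, yet its own imputed date is Day 31.
- If dosing dates are spread evenly over the year (assumption), 30 × 29/365 = 2.4 of 30 subjects would have such a dosing date. This counts dosing dates, not wrong flags. A wrong flag also needs a month-only event in the next month.

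**Opposite error.** The closest the second following month can come is dosing on 31 January of a non-leap year, when 1 March is Day 30. No day of that month ever falls on or before Day 29, so the rule never labels a true treatment-emergent event as post-treatment.

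**Sensitivity to the cut-off.** In an ordinary year the next 1st is Day 30 for 11 of the 29 dates, Day 31 for 11 and Day 32 for 7. Certain errors by cut-off:

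- Day 29: 29 dates
- Day 30: 11 + 7 = 18 dates
- Day 31: 7 dates
- Day 32: none

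A cut-off before Day 29 would add dates.

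**The case against.** The strongest reply concerns the boundary. Protocol 12.3.1.3 places post-treatment events after visit 6, and Protocol 6.1 gives visit 6 a window of Day 29 ± 3 days. If the period ends at the actual visit, and that visit took place on Day 32, none of the adverse event cases is a certain error. This stands as a limit on the point. It does not remove it, because the SAP's own definition says Day 29 and its month rule refers to neither that day nor the visit.

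The adverse event rule is also conservative. It can only add treatment-emergent events, and Day 29 is already generous: five half-lives of about 100 hours are 500 hours, or 20.8 days. SAP 4.8.1 also tabulates all, pre-treatment and post-treatment events, so no event is lost. That is correct and keeps the consequence small. It does not help the drug rule, where classing a finished course as concomitant is simply wrong.

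A reader might infer more than the documents support:

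- **That a large share of pre-study treatments is misclassified**, because much of the 30-day look-back falls in the dosing month. The documents give no rate of month-only dates. A course completed before dosing must also have begun earlier, and so more often in the previous month, which the rule already treats as pre-treatment.
- **That affected drugs vanish from the prior-medication table.** SAP 4.1.3 does not say that the concomitant label removes them. A record with a pre-dose stop meets the SAP 4.4 definition of prior on its face.
- **That all treatments ended before imlifidase are affected.** Only those with a month-only start in the dosing month and a stop date that clearly precedes dosing are.

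**Conclusion.** The point holds as a minor internal inconsistency, in two parts.

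- **Drugs:** a month-only start in the dosing month with a recorded stop clearly before imlifidase is classed against SAP 4.4 and given an impossible start date. No check in the SAP catches it.
- **Adverse events:** for 29 of 365 dosing dates (7.9%) the flag for a next-month event contradicts both the Day 29 limit and the imputed date. This assumes that Day 29 is the dosing date + 28, as the SAP's wording implies, and not the actual visit 6 date. The error can only over-count.

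The number of affected records cannot be estimated from the documents. It is probably small and may be zero, since each error needs a partial date of a particular kind. The study is single-arm and descriptive with no testing, and the listings show partial dates as reported, so no main conclusion depends on this. Where the order of events is truly unknown, for example when the stop is also known only to the dosing month, the current default is defensible.

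**What to change.** Amend SAP 4.1.3 in three places:

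1. If a recorded stop date, complete or partial but unmistakably earlier, precedes the start of imlifidase, class the record as prior (drug) or pre-treatment (event). The imputed start may not fall after that stop.
2. Flag a month-only event start as treatment emergent only if at least one day of that month and year lies between the start of imlifidase and Day 29. Otherwise it is post-treatment emergent. State that Day 29 is the nominal study day.
3. Extend the consistency check to imputed start dates against recorded stop dates.

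Records whose order cannot be known keep the present default.

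The cost is a few sentences and a few lines of derivation code, with no new data. The downside is that a few records move between tables. Version 2.0 of the SAP was finalised during the main analysis, so the change should be documented. It can be applied in the planned CSR addendum and explained in the CSR as a deviation, which SAP section 1 allows.

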## 4.2 Subject disposition

Subjects enrolled but not dosed will be regarded as screening failures.

Subjects screened but not found eligible will be stated in the trial report but otherwise not accounted for.

A table will present the subject disposition as number of subjects screened, enrolled, GBS not confirmed at 6 months, GBS not confirmed at 12 months, screen failures, completed (6 months follow-up visit and 12 months follow-up visit, respectively), withdrawn overall and by reason for withdrawal and by subjects in each of the analysis sets.

## 4.3 Protocol deviations

Deviations from the protocol, as continuously tracked by investigator and sponsor, will be classified as 'minor' or 'major'. The final classification of the deviations will be done before the database lock.

All protocol deviations will be summarised with frequency and percentage for each category of protocol deviation, for both FAS and safety analysis sets. The protocol deviations will also be listed by subject.

## 4.4 Demographics and other baseline characteristics

The demographics are age at screening date, sex, and race.

Medication will be classified according to WHODrug Global B3 dictionary version 2018Q3.

Summary tables will be performed for:

- Demographics (including age (years), sex, race, height, weight and BMI before IMP intake)
- Medical history or concomitant illness as reported at study entry
- Baseline GBS characteristics and GBS symptoms, including:
  - Presence of diarrhoea (<4 weeks from screening)
  - Onset of weakness due to GBS
  - Days from onset of weakness until imlifidase administration
  - GBS variant type at screening
  - Electrophysiology classification of subtype the subject has according to JJ Sejver et al. (Vaccine 2011; 29: 599-612)
  - Status of cranial involvement
  - Medical history of disease affecting mobility (yes/no)

- Medical history of disease affecting respiration (yes/no)
- Pre-medication to prevent/minimise risk of infusion reactions (methylprednisolone and antihistamine or an equipotent antihistamine) before imlifidase infusion
- Medication to minimise the risk for bacterial infections (prophylactic antibiotics), summarizing all prophylactic antibiotics the subjects had during the first 14 days after imlifidase administration (including prophylactic antibiotics given in day before imlifidase administration and in same day as the imlifidase administration).
- Prior medication, summarizing all medications the subjects had before the study (prior to start of study treatment)
- Concomitant medication, summarizing all medications the subjects had throughout the study (following start of study treatment), considering the following tables:
  - All concomitant medications
  - Concomitant medication during Day 1 – 29
  - Concomitant medications during Day 30 – End of study

Note: prior and concomitant medication will exclude ‘Pre-medication to prevent/minimise risk of infusion reactions before imlifidase infusion’ and ‘Medication to minimise the risk for bacterial infections’.

Listings will be provided including the values for each subject of:

- Subject disposition (enrolled, completed, withdrawn (reason for withdrawal) for each analysis set (FAS, SAF and PKPDAS).
- Demographics (including age (years), sex, race)
- Medical history as reported at study entry (system organ class (SOC) and preferred term (PT))
- GBS disease information at study entry
- Baseline GBS characteristics
- Pre-medication to prevent/minimise risk of infusion reactions (methylprednisolone and antihistamine or an equipotent antihistamine) before imlifidase infusion
- Prophylactic antibiotics (flag in if during the first 14 days after imlifidase treatment).
- Prior medication (anatomical therapeutic chemical (ATC) code and generic drug name)
- Concomitant medication (anatomical therapeutic chemical (ATC) code and generic drug name)
- Serology (HIV-1 and HIV-2 antibodies, hepatitis B surface-antigen and hepatitis C virus antibodies performed at screening)

## 4.5 Compliance and exposure

A summary table will be presented for exposure and compliance. The table will summarise the exposure (total dose of imlifidase, actual dose of imlifidase in mg/kg, total grams of IVIg given per dose, total grams of IVIg given to the subject, number of IVIg doses) and compliance (percent of planned dose of imlifidase compared to actual, percent of number IVIg doses compare to planned\*).

\*As per protocol, all subjects are planned to receive standard care with IVIg infusion (0.4 g IVIg/kg/day for consecutive 5 days).

Compliance and the drug exposure will be also presented in a listing by subject. In addition, listings will be presented to show drug administration details of imlifidase and IVIg.

## 4.6 Subgroups

If deemed appropriate, the following subgroups might be considered for specific subgroup analysis. If so, the subgroup analysis will be defined at a later stage in a separate document.

The following subgroups might be considered:

- [REDACTED]
- Electrophysiology classification subgroup: subjects with acute motor axonal neuropathy (AMAN)/ acute motor and sensory axonal neuropathy (AMSAN) and subjects with acute inflammatory demyelinating neuropathy (AIDP).
- [REDACTED]

The above defined subgroups will be listed and summarized (number and percentage of subjects in each category of subgroup) on the FAS.

## 4.7 Efficacy analysis

### 4.7.1 GBS Disability Score (GBS DS)

The GBS Disability Score (GBS DS) used for the efficacy endpoints will be assessed for all subjects as per the schedule of assessments. The score is defined as follows:

0 = Healthy

1 = Minor symptoms and capable of running (subjects must be asked to run)

2 = Able to walk independently 10 meters or more but unable to run

3 = Able to walk more than 10 meters across an open space with help

4 = Bedridden or chair bound

5 = Needing mechanical ventilation

6 = Dead

Summary statistics will be presented in tables for the actual values and absolute change from baseline by time point. Also, shift tables will be presented to show the change from baseline as compared to post-baseline visits for the GBS DS.

In addition, the number and percentages of subjects with improvement of at least one, two or three grades, respectively, on the GBS DS will be presented by time point.

Similarly, the number and percentage of subjects able to walk unaided (GBS DS  $\leq 2$ ) and run (GBS DS  $\leq 1$ ), respectively, will be presented by time point.

Lastly, the following Kaplan-Meier analysis summary tables and plots will be presented:

- Time to improvement by at least one grade on the GBS DS
- Time to improvement by at least two grades on the GBS DS
- Time to improvement by at least three grades on the GBS DS
- Time to walk independently (GBS DS  $\leq 2$ )
- Time to run (GBS DS  $\leq 1$ )

Study end/discontinuation will be considered as censoring for subjects that do not have the event. In addition, the survival function will start at 0, since all these are “positive” events.

For each endpoint two separate Kaplan-Meier plots will be presented, one up to Day 29 (collected part of Visit 6) and one up to Day 360 (collected as part of Visit 10), including the subjects at risk at specific timepoints. Also censored observations will be marked as such on the plot.

The summary tables for the corresponding Kaplan-Meier analysis will include the following for specific timepoints up to Day 360: subjects at risk, number of subjects with events, censored observations, proportion estimates and associated pointwise 95% confidence interval (CI).

A separate table will present the number of subjects included in the analysis with corresponding number of events, number of censored observations and summary statistics for the time to event (minimum, maximum, median and associated 95% CI, quartiles).

Additionally, a swimmer plot will be created to show change in GBS DS over time up to Day 92 (collected as part of Visit 8). Subjects will be shown as rows on y-axis, time on x-axis, each subject having a bar that is coloured according to latest GBS DS.

